### *Exclusion criteria for all Participants:*

- History of head trauma with LOC > 30 minutes, or with a penetrating head wound, or with moderate to severe memory or other cognitive impairment.
- Neurological disorders: multiple sclerosis, epilepsy, stroke, PD, other degenerative CNS disorders, or neuropathy with radicular involvement.
- Acute or chronic major psychiatric disorders: schizophrenia, bipolar disorder or severe major depressive disorder, or severe anxiety disorder except PTSD and panic disorder (PTSD and depressive symptoms are common co-morbid conditions for combat mTBI and a subset of these patients have symptoms consistent with panic disorder as well).
- Use of illegal drugs; alcohol abuse within the past 6 months.
- Poorly controlled hypertension, heart failure, coronary heart disease, peripheral artery disease, carotid artery disease, diabetes mellitus, pulmonary disease with hypoxia or hypercapnia,

significant hepatic disease or hepatitis C seropositivity, renal failure, treatment for cancer, HIV positive, active infectious disease or presence of abdominal aortic aneurysm.

- Contraindications to LP (e.g., spinal cord injury; deformity, severe disease or infection in the region of the lumbosacral spine; bleeding tendency, use of anticoagulant medications, or platelet count <100,000/mm^2).
- Receiving medication in an investigational drug study.
- Exclusionary medications (used in the 4 weeks prior to screening):
  - Fibrates and niacin due to increased risk for myopathy in combination with statins;
  - Potential drug-drug interactions with statins via effects on CYP3A4: itraconazole, ketoconazole, erythromycin, clarithromycin, HIV protease inhibitors, nefazodone, amiodarone, cyclosporine, isoniazid, quinidine, or large quantities of grapefruit juice (>1 quart daily);
  - Selected CNS-acting medications: antipsychotics, anti-Parkinson's disease medications and CNS stimulants
  - Other medications affecting coagulation and/or inflammation: coumadin, potent anti-inflammatory medications (hydrocortisone, methotrexate or other potent immune-modulating medications), and anti-HIV medications.
- All female subjects of childbearing potential will undergo a urine pregnancy test at every subject visit; subjects with positive pregnancy test results will be excluded. In addition, all female subjects of childbearing potential will be required to use a reliable method of contraception throughout the duration of the study.

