### **Study procedures:**

There will be a total of nine study visits over a period of 12 months, including the screening visit, four visits for monitoring adverse effects and compliance, and four visits for measuring study outcomes (two at Baseline and two at 12 months). Table 3 below outlines all study visits.

Screening visit: Screening for eligibility will include a brief cognitive screen with the Montreal Cognitive Assessment (MoCA). Detailed medical and psychiatric history, current medications, and medications used over

past 6 months will be reviewed. Potential participants will be administered the Structured Clinical Interview for DSM-IV--Patient Edition (SCID-IV) to diagnose exclusionary psychiatric disorders.

Table 3. Detailed Schedule of Study Visits

	Screen Visit	Baseline Visits		Safety Visits				12 mo Outcome	
		1 st	2 nd	6 wk	3 mo	6 mo	9 mo	1 st	2 nd
Demographics	X								
Medical/psychiatric/military history	X								
Physical/neurological examination	X							X	
CBC, Chem 7, TSH, B12, folate, albumin, routine urinalysis	X								
fasting lipid panel (HDL, LDL, triglycerides)	X	X						X	
Plasma homocysteine & C-reactive protein (CRP)		X						X	
LFTs, bilirubin, CPK, HbA1c	X			X	X	X	X	X	
Urine pregnancy test	X	X	X	X	X	X	X	X	X
APOE genotype	X								
LP – CSF biomarkers		X						X	
SCID-IV	X								
CAPS, SWLS			X						X
PCL-M, PHQ-9, AUDIT-C			X	X	X	X	X		X
MoCA	X		X	X	X	X	X	X	
Neuropsychological test battery			X						X
Vital signs	X	X	X	X	X	X	X	X	X
Review of concurrent medications	X	X		X	X	X	X	X	
Assess adverse events			X	X	X	X	X	X	X
Pill count for med compliance				X	X	X	X	X	
Dispense study medications			X	X	X	X	X		

A complete physical and neurological examination will be performed. Screening laboratory tests will be obtained, including complete blood count (CBC), chemistry panel, thyroid stimulating hormone (TSH), vitamin B12, folate, SGOT, SGPT, SGGT, bilirubin, alkaline phosphatase, CPK, albumin, and fasting lipid panel (total cholesterol, HDL, LDL, and triglycerides), urinalysis, and (in female subjects of childbearing potential) a urine pregnancy test. Blood samples will also be collected for apolipoprotein E (APOE) genotyping (described below). A urine sample will be obtained for routine urinalysis and (in female subjects of childbearing potential) a urine pregnancy test.

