**Baseline:** The Baseline visit will be scheduled within 4 weeks of the Screening visit. The Baseline visit consists of 2 separate appointments within a week of each other. During the first visit, vital signs will be obtained, a brief physical examination will be performed, concurrent medications will be recorded, a blood draw will be performed for measurement of plasma lipids and inflammatory markers, and an LP will be performed as described in detail below.

During the second baseline visit, the neurocognitive test battery will be administered and behavioral assessments will be performed. Comorbid PTSD will be assessed with the CAPS. A detailed description of all study instruments is below.

**Randomization, titration, and continued study treatment:** Upon completion of all baseline procedures, participants will be randomized to receive simvastatin or placebo. Stratification factors will include age (<40 vs ≥ 40 years), gender, and number of blast trauma exposures (<5 and ≥5). Permuted block randomization will be used within each stratum. Varying the block size reduces the predictability of treatment assignment. Separate blocked sequences will be generated for each of the three strata and provided directly to the Research Pharmacist at the VA Puget Sound, who will prepare study drug for dispensing.

Simvastatin will be started at 20 mg qhs and titrated over 2 weeks to a final dose of 40 mg qhs. Placebo will be titrated at week 2 correspondingly. We assume a drop-out rate of ten percent, yielding a total sample size of 50 subjects per group at the end of the study.

**Safety and compliance visits:** Four additional visits will be scheduled at 6 weeks and at 3-, 6-, and 9-months of treatment to monitor adverse effects, assess compliance with study medications, and dispense study medication. Each visit will include measurement of vital signs, update of concurrent medications, and any self-report of adverse effects. Pill counts will be used to assess compliance. Safety assessments as described below will be performed.

**Outcome assessment:** Outcome assessments will be obtained in two visits at the end of 12 months of treatment. Procedures for outcome assessments duplicate the procedures performed during the Baseline visits as described above. Pill counts will be used to assess compliance with medication use.

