### **Biomarkers:**

Overview: The primary outcome measures are biomarkers in CSF: t-tau, p-tau181, p-tau181:t-tau ratio, and BDNF. The secondary outcomes are additional CSF biomarkers of amyloid dysregulation: A $\beta$ 42; oxidative stress: F2-isoprostanes; and neuroinflammation: IL-6, IL-8, and S100 $\beta$ . All subjects will also undergo APOE genotyping. For each substance measured in CSF or blood, all study samples (i.e., from the baseline and from the 12 month follow-up visit) from any one subject and equal numbers of samples from subjects in the statin and placebo groups will be assayed within a single assay to reduce inter-assay variability. All samples will be measured blind to treatment assignment.

Blood collection for DNA and plasma and serum biomarkers: On the day of LP at baseline and at the 12 month follow-up visit, subjects will undergo blood collection for plasma and serum for biomarkers. Thirty five ml of blood will be collected into pre-chilled tubes containing EDTA and placed on ice. These samples will be cold centrifuged within one hour of collection, aliquoted into polypropylene tubes and frozen at -70 degrees C until assayed. Twenty ml of blood will be collected into plain glass tubes and sent to the VA Puget Sound clinical laboratory for the measurement of total cholesterol, HDL, LDL, homocysteine, and C-reactive protein (CRP).

At the screen visit only, 30 mls of blood will be collected into unchilled tubes containing EDTA and sent to [name] laboratory at VA Puget Sound for DNA preparation and APOE genotyping. Clinical lab analysis will take place at VA Puget Sound. All plasma and serum samples for biomarker analysis will also be accessioned, inventoried, and stored at -70 degrees C at VA Puget Sound S until assayed.

APOE genotyping will be performed by the UW ADRC Genetics Core under the direction of [name]. APOE genotyping will be performed using previously described PCR conditions and the HhaI restriction digest method.

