## PROTECTION OF HUMAN SUBJECTS

### (1) Risk to Subjects

(a) Human Subjects Involvement and Characteristics: Participants will be 120 Iraq and Afghanistan Veterans between the ages of 21 and 50 who are in good general health and who meet the specific study inclusion/exclusion criteria as described in detail in the "Research Design and Methods" section above. Persons of all races and ethnicities and both genders will be eligible. Participants will be naïve for statins, and will have either normal LDL cholesterol or mildly elevated LDL cholesterol which does not require drug therapy per NCEP/ATP-III guidelines.

Specific inclusion criteria include documented hazardous duty in Iraq and/or Afghanistan with the U.S. Armed Forces and exposure to blast concussion (with >6 months since last blast exposure) sufficient to meet ACRM criteria for mTBI (*described in detail above*). Participants will have a BMI between 18 and 36 (BMI outside this range may affect the biomarker measurements and increase difficulty of LP).

Exclusion criteria for all participants will include: penetrating head wound; seizure disorder; insulin-dependent diabetes; alcohol abuse or other substance abuse; DSM-IV diagnosis of schizophrenia or other psychotic disorder, bipolar disorder, or dementia; use of exclusionary medications (used in the 4 weeks prior to screening) or receiving any investigational medication; contraindication to LP (spinal deformity, severe lumbar spine disease or infection at LP site, bleeding tendency or on anticoagulant medication); platelet count less than 100,000 at time of LP.

Women of childbearing potential must have a negative pregnancy test at screen and must agree to use an acceptable form of birth control for the duration of the study. We suggest that women continue to use birth control for one full menstrual cycle after completing or withdrawing from the study.

It is likely that economically disadvantaged subjects will participate in this study. This may be considered a vulnerable population. While subjects will receive up to \$650 for completion of the study, it is not felt that degree of remuneration will represent any form of economic coercion to those that are economically disadvantaged, considering the potentially significant time commitment we are asking the subjects to make. Prisoners and institutionalized individuals will not be involved in this study.

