**Risks of Lumbar Puncture:** The risk of serious effects from LP (infection, nerve root damage) is extremely low. Rarely, patients may experience transient local pain either at the site of the puncture or in the distribution of the sciatic nerve if the nerve roots of the *cauda equina* are stimulated. Because the LP is performed well below the termination of the spinal cord and because the nerve roots readily move aside from the spinal needle, the possibility of permanent damage to a nerve root is very remote. Subjects with blood clotting abnormalities, on anticoagulant medications, or with inadequate platelet function will be excluded. A previously common (approximately 20% in young persons) adverse effect was post-LP headache. The incidence of headache is a function of the diameter and type of spinal needle used and not the amount of fluid removed. Prior to the past 8 years, our method of using a very fine 25g Quincke (cutting) spinal needle reduced the incidence of post-LP headache to less than 5%. Over the past 8 years, we have instituted use of the 24g Sprotte atraumatic spinal needle. The Sprotte needle has been recommended in recently published guidelines for reducing risk of post-LP headache. We have performed over 300 LPs since we began using the Sprotte spinal needle and in our hands, risk of post-LP headache is now less than 1%, similar to that reported in the literature for the 24g Sprotte needle.

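### The only scheduled platelet count is at screening, so the 12-month research lumbar puncture relies on a count about a year old

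*Combined protocol and SAP*

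**What the plan says.** **The limit.** Under Exclusion criteria for all Participants, the contraindications to LP include "bleeding tendency, use of anticoagulant medications, or platelet count" below 100,000. Protection of Human Subjects, (1) Risk to Subjects, part (a), ends its list of exclusions with "platelet count less than 100,000 at time of LP". The LP risk text in the same section adds: "Subjects with blood clotting abnormalities, on anticoagulant medications, or with inadequate platelet function will be excluded". That last sentence concerns platelet function rather than the count, so it supports the intent but does not restate the numerical limit.

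**The test.** In Table 3 the row "CBC, Chem 7, TSH, B12, folate, albumin, routine urinalysis" is marked once, at the screening visit. The accompanying text agrees: "Screening laboratory tests will be obtained, including complete blood count (CBC), chemistry panel". The LP row is marked twice, at the first baseline visit and the first 12-month visit.

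**The timing.** "The Baseline visit will be scheduled within 4 weeks of the Screening visit". The two baseline appointments fall within a week of each other, and randomization follows completion of baseline. For the 12-month visits, "Procedures for outcome assessments duplicate the procedures performed during the Baseline visits as described above".

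**The concern.** A contraindication to a procedure matters each time the procedure is done. Here the limit can be checked against a recent result before the first LP but not before the second. The section on potential benefit states that subjects gain nothing from the LPs themselves, so a safety limit that the sponsor has set should be verifiable on both occasions.

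The protocol does schedule a test before each LP when it means to. The text on reducing LP risks requires a negative urine pregnancy test in women of childbearing potential before any LP, and Table 3 places that test at both LP visits. The platelet limit has no matching entry at 12 months. What is at stake is procedural safety at the second LP, not the validity of the trial's conclusions.

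**Working it through.** The documents state no age for the platelet count, so there is no figure of the plan's own to reproduce. The age follows from the schedule.

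**1. Does any other scheduled test supply a platelet count?**

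- Clinical blood tests on the LP day (Biomarkers): 20 ml is "sent to the VA Puget Sound clinical laboratory for the measurement of total cholesterol, HDL, LDL, homocysteine, and C-reactive protein (CRP"). The other 35 ml is spun and frozen for later assay. No CBC.
- Safety bloods (Protection Against Risk; Table 3): liver function tests, CPK and HbA1c. No CBC.
- 12-month procedures: a repeat of baseline, which contains no CBC.
- The cell count described under lumbar puncture is performed on CSF, not blood.

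The screening CBC is therefore the only scheduled source.

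**2. Age of the count at each LP.**

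Inputs, from Baseline, Randomization and Outcome assessment: screening to first baseline visit, 0 to 4 weeks; first to second baseline appointment, 0 to 1 week; treatment, 12 months, taken as 52 weeks.

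- Baseline LP (first baseline visit): 0 to 4 weeks.
- 12-month LP, minimum: 0 + 0 + 52 = 52 weeks.
- 12-month LP, maximum: 4 + 1 + 52 = 57 weeks. If the 4-week limit is read as covering both baseline appointments, 4 + 52 = 56 weeks.

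**3. Number of LPs affected.**

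- Sample Size, Effect Size, and Power: 120 × (1 − 0.17) = 99.6, or about 100 completers.
- Randomization: a 10% drop-out would give 120 × 0.90 = 108, but the same sentence concludes with 50 per group, which is 2 × 50 = 100. I therefore use about 100.
- Early termination could add to this. The discontinuation visit is meant to collect outcome measures, and the secondary mixed model uses early-termination data, but no text says that an LP is done then. The ceiling for second LPs is 120.

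**4. Would the 9-month safety bloods serve?** Nine months is about 39 weeks, and 52 − 39 = 13 weeks. A count taken then would still not be current at the LP.

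**The case against.** The strongest reply is that all three statements describe who is excluded from the study. The phrase in Risk to Subjects closes an entry-exclusion list. Read as an entry rule, the schedule applies it properly: a screening CBC, then a baseline LP within about 4 weeks. A reader might infer that the schedule breaches the protocol's own rule at 12 months. The documents do not support that, because the entry-only reading is open. Nor do they forbid an unscheduled count, and wording tied to the time of the LP may even imply one. What remains is that a stated contraindication to LP has no scheduled test behind it at the second LP, whichever reading is right.

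A second reply is that the risk is low. Subjects are aged 21 to 50 and in good general health. Entry criteria remove significant hepatic disease, hepatitis C, HIV, cancer treatment, bleeding tendency and anticoagulants. The common simvastatin effects listed are raised transaminases, myalgia and raised CPK, not low platelets. Serious LP effects are described as extremely low. All of this stands, and it sets the importance of the point.

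A third reply is that other checks exist. Examination, medication review and adverse-event review fall at the 12-month LP visit. Subjects are asked to tell staff before starting a new medicine, and liver tests are repeated at four visits before that one. These reduce the residual risk, but none gives a platelet count. The 12-month liver tests are drawn at the LP visit itself with 24 hours allowed for review, and the clinician's call comes after the puncture.

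Finally, since the 12-month LPs are nearly half of those planned, a reader might infer that nearly half carry added risk. They do not: that share reflects testing before only the first of two LPs and says nothing about bleeding.

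**Conclusion.** The gap is real and minor. Followed as written, the schedule takes about 100 subjects to a second research LP on a platelet count roughly 52 to 57 weeks old, against at most about 4 weeks at the first. The range assumes that 12 months is 52 weeks, that treatment starts when baseline is complete, and that the LP falls at 12 months, since no visit window is given.

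The documents give no rate of new low platelets or of bleeding after LP. The number of subjects who would be below 100,000 at 12 months is therefore unknown and, given the entry criteria, probably very small; I offer no estimate. Power and the planned analyses are not materially affected.

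**What to change.** 1. Add a CBC or platelet count to Table 3 for the 12-month LP, with the result seen before the puncture. A small tube could be added to the LP-day draw of 35 + 20 = 55 ml, which already precedes the LP, or a sample could be taken shortly before. The existing 24-hour laboratory review would not by itself ensure that the result is seen in time.
2. State that, if the count is below 100,000, the LP is omitted and the remaining 12-month measures are completed.
3. Apply the same check to any LP done at early termination.
4. Keep the present wording in Risk to Subjects, which ties the limit to the time of LP, and state that it applies to each LP. A fixed 4-week window in its place would loosen it.

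The cost is one extra CBC per completer, about 100 in all, with no extra visit if taken at the LP-day draw, and a possible short wait for the result. The downside is a rare missed 12-month CSF sample. As an illustration, losing one of 100 would widen the standard error by a factor of about √(100/99) = 1.005.

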
### *Inclusion Criteria for all participants:*

- Males and females ages 21-50 years.
- Documented hazardous duty in Iraq and or Afghanistan with the U.S. Armed Forces.
- Exposure to one or more blast trauma events resulting in mTBI according to ACRM criteria as defined above.
- More than 6 months since last blast trauma exposure
- Ability to complete psychometric and other clinical assessments in English (i.e., adequate English language skills, vision and hearing).
- Normal or mildly elevated cholesterol which does not require drug therapy based on NCEP/ATP-III guidelines (i.e., fasting LDL <190 for those with  $\leq 1$  cardiovascular risk factor and < 160 for those with 2+ risk factors).
- No use of statins during the previous year and no recent (past 4 weeks) use of other lipid-lowering drugs (e.g., fibrates, niacin > 500mg/d, or high dose omega-3 fatty acids) preceding randomization.
- No clinically significant laboratory abnormalities (electrolytes, glucose, carbon dioxide, BUN, creatinine, vitamin B12, folate, albumin, thyroid stimulating hormone).
- Platelet count > 100,000/mm^2.
- Body Mass Index (BMI) between 18 and 36 inclusive (BMI outside this range would affect biomarker measurements or make LP difficult to perform).

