Description of Recruitment Process: Participants will be recruited from the MIRECC Mild TBI/Behavioral Specialty Clinic; Deployment Health Clinic, Polytrauma Clinic, General Internal Medicine Clinic, and Mental Health Clinics at VA Puget Sound; the Seattle downtown Vet Center; community-based outpatient clinics (CBOCs), and from outreach to National Guard and Reserve units. Recruitment will be assisted by posters, flyers, brochures, announcements in the VA daily bulletin, and print and radio media advertising. Prospective participants will have their charts reviewed by referring providers to screen for exclusionary medical conditions and medications.

Potentially eligible persons will be referred to the study team for obtaining informed consent. Written informed consent will be obtained from participants by the PI, study Co-Investigator, or Study Coordinator. If a potential participant's primary mental health care provider is a study investigator, another investigator will conduct the consent process. Care will be taken to assure participants that research study participation is voluntary and their current treatment and future services and benefits are not contingent on participation in this or any research study.

Participants will receive compensation for their time and inconvenience as follows: \$50 for the screening visit, \$50 for each cognitive testing day, \$200 for each LP day, and \$25 for each safety visit. The total each subject will receive if all study visits are completed is \$650. Subjects who withdraw early or are withdrawn from the study will receive pro-rated payments based on the number of study visits completed.

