(b) Sources of Materials: Research materials from living human subjects will be results from clinical/neuropsychiatric assessments; blood samples collected for screening labs, DNA, and biomarker analysis; and CSF collected for biomarker analysis. These procedures will be done specifically for research purposes. In addition, existing medical records will be reviewed to confirm eligibility for participation. Consent will be obtained before reviewing existing medical records.

(c) Potential Risks: Risk to subjects is modest. All risks are research risks, none are therapeutic risks. They include possible stress from undergoing clinical/neuropsychiatric assessment, risks of blood draw/i.v. placement, LP, risks of taking simvastatin, and potential loss of confidentiality.

*Risks of Simvastatin*: Simvastatin is used widely for lowering cholesterol and for primary prevention of cardiovascular and cerebrovascular disease at the doses proposed in this application. It is generally safe and well tolerated. The most common adverse effects in clinical use are elevated liver transaminases, myalgias, and elevated CPK. However, the literature suggests that the rate of adverse reactions necessitating withdrawal from statin therapy is less than one percent in clinical practice. Simvastatin is classified by the US FDA as Pregnancy Category X and is contraindicated in women who are pregnant or nursing. All female subjects of child bearing potential will have urine pregnancy tests at every study visit, will be required to be using a reliable form of contraception, and will be told of the risks of becoming pregnant while participating in this study. We also advise women of childbearing potential that they wait one full menstrual cycle after stopping the medications offered in this study before becoming pregnant.

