**(b) Protection Against Risk:**

*Reduction of risks related to simvastatin:* All study participants will have either normal or mildly elevated cholesterol not meeting current NCEP guidelines for treatment with cholesterol lowering medications. Simvastatin has been widely used for primary or secondary prevention of cardiovascular diseases. Although we will treat subjects with non-elevated cholesterol, adverse effects related to excessively low cholesterol levels are not anticipated, as recent trials with high doses of potent statins producing very low levels of LDL-cholesterol have shown that such low LDL-cholesterol serum levels are generally safe and, in fact, are associated with improved clinical outcomes in terms of coronary artery disease.

Simvastatin is classified by the US FDA as Pregnancy Category X and is contraindicated in women who are pregnant or nursing. All female subjects of child bearing potential will have urine pregnancy tests at every study visit and will be told of the risks of becoming pregnant while participating in this study. We consulted with pharmacist at VA Puget Sound whether a woman should wait for a certain period after ceasing statin drug before becoming pregnant and he suggested 16 days (the elimination half-life of radioactive simvastatin plus metabolites in humans is 4.5 hours. Assuming 95% of the drug and metabolites are eliminated after 5 half-lives, then 16 days could be considered safe). We are erring on the safe side and suggesting that women of childbearing potential wait one full menstrual cycle after stopping the medications offered in this study before becoming pregnant. Contraception is not required for male participants.

At randomization, subjects will be advised of potential drug-related side effects from simvastatin such as muscle pain and weakness and nausea or vomiting. They will be counseled on the importance of letting the study personnel know which medications they are currently taking and that they should inform the study staff before initiating any new medication treatment. Subjects will be told that many medications should not be taken with simvastatin and that they should not drink large quantities of grapefruit juice while in the study (as intake of large quantities of grapefruit juice may result in elevated simvastatin serum levels). Subjectst will also be advised to avoid drinking excessive amounts of alcohol.

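### The protocol states that simvastatin is contraindicated in nursing women, but the eligibility criteria cover only pregnancy, so a nursing woman could be randomised as written

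*Combined protocol and SAP*

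**What the plan says.** Section (1)(c), Potential Risks, under Risks of Simvastatin, says that the drug "is contraindicated in women who are pregnant or nursing". Section (2)(b), Protection Against Risk, says so again: "Simvastatin is classified by the US FDA as Pregnancy Category X and is contraindicated in women who are pregnant or nursing".

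The inclusion criteria admit "Males and females ages 21-50 years". In the exclusion criteria, women of childbearing potential are tested for pregnancy at every visit, "subjects with positive pregnancy test results will be excluded", and they are "required to use a reliable method of contraception throughout the duration of the study". The summary in section (1)(a), Human Subjects Involvement and Characteristics, asks for a negative pregnancy test at screening and says that such women "must agree to use an acceptable form of birth control for the duration of the study". That summary points back to Research Design and Methods for the detailed criteria, so the list there is the operative one.

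The exclusion list has an entry headed "Contraindications to LP". It has no matching entry for contraindications to simvastatin.

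**The concern.** The protocol names two groups of women who should not receive the study drug, and its criteria keep out only one. The gap is most visible in section (2)(b), which exists to reduce the risks of simvastatin. After repeating the contraindication, it sets out pregnancy testing, counselling about becoming pregnant, and a waiting period before conception. None of these deals with nursing.

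Staff who learn that a candidate is nursing have the contraindication in the risk text but no criterion under which to exclude her. Staff who do not ask may never learn of it. There is also no lipid indication to set against the exposure: participants must have cholesterol that does not call for drug treatment, and section (1)(c) classes all risks of the study as research risks.

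**Working it through.** This point concerns eligibility text, and the plan states no figure to reproduce. The check compares what each relevant section says on pregnancy and on nursing.

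| Section | Pregnancy | Nursing |
|---|---|---|
| Risks of Simvastatin, (1)(c) | Contraindicated | Contraindicated |
| Protection Against Risk, (2)(b) | Contraindicated; tests and counselling follow | Contraindicated; no measure follows |
| Inclusion criteria | Not mentioned; women 21 to 50 admitted | Not mentioned |
| Exclusion criteria | Positive test excludes; contraception required | Not mentioned |
| Summary of criteria, (1)(a) | Negative test and birth control required | Not mentioned |
| Screening visit and Table 3 | Urine test at 9 of 9 visits | Not mentioned |
| Criteria for termination from study | Positive test removes | Not mentioned |

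**Do the pregnancy measures cover nursing?** No. A nursing woman can have a negative pregnancy test and use reliable contraception.

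**Does a general clause cover it?** No. The exclusion list handles statin risk item by item: fibrates and niacin, CYP3A4 interactions, significant hepatic disease, pregnancy. It has no clause for contraindications to the study drug and none for investigator discretion.

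**Do the screening safeguards cover it?** Only by chance. Prospective participants have their "charts reviewed by referring providers to screen for exclusionary medical conditions and medications" (Description of Recruitment Process), and medical records are checked for eligibility (section (1)(b)). Both steps look for listed criteria, and nursing is not one. The history and full physical examination at screening could reveal it, but no rule follows from the finding.

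**Is a later check needed?** No. Baseline falls within 4 weeks of screening and its two appointments within 1 week of each other, so randomisation comes at most about 4 + 1 = 5 weeks after screening. A woman who conceived later would be caught by the test at each visit and removed. The termination criteria therefore need no change.

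**Size.** The documents give no number of women or of nursing women. Inclusion of Women and Minorities says that women should be fewer than 25% of Military Police participants and that the other three named specialties are all male. For illustration only, assume that k nursing women enrol, with equal and independent allocation. The chance that at least one receives simvastatin is 1 − 0.5^k:

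- k = 0: 0%
- k = 1: 50%
- k = 2: 1 − 0.25 = 75%

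Allocation is in fact by permuted blocks within strata that include gender, and the block sizes are not given. If two such women fell in the same block, the figure would be 1 − (2/4)(1/3) = 83% for an assumed block of 4 and 100% for an assumed block of 2. For k = 2 the illustration therefore runs from 75% to 100%, depending on the blocks.

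**The case against.** The strongest reply is that unnoticed enrolment is unlikely. The contraindication is stated outright, twice, so staff who know that a candidate is nursing have the information they need. Chart review, medical history, medication review, physical examination, pregnancy testing and contraception counselling are all occasions on which recent childbirth would naturally come up. Few women will enrol and fewer still would be nursing. Table 3 is a schedule of procedures, so its silence on nursing proves little, and its medical-history row is where such a question would sit. The consent pages are not in the reviewed file and may address nursing.

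Much of this stands as a limit on size. The gap is a missing criterion and a missing prompt to ask; the protocol is not silent on the contraindication itself. But none of these steps expressly asks about nursing, and a screener who applied the written criteria exactly would have to accept the candidate. What the consent form says is unknown and is not counted here. It would not alter the eligibility list in any case.

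**Conclusion.** The concern holds. Applied as written, the criteria admit a woman whom the protocol itself says should not receive the study drug. The likely number is very small and may be zero. For a nursing woman allocated to simvastatin, exposure would start at 20 mg nightly, rise over 2 weeks to 40 mg, and last as long as she nursed, up to the 12-month treatment period. The documents do not quantify the risk to a nursing infant, and no estimate is offered here. The sample size, endpoints and analysis are untouched.

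The conclusion rests on the protocol's own statement of the contraindication and on the eligibility text. It does not depend on the illustrative probabilities. The change should be made, because a stated contraindication ought to have a criterion that enforces it.

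**What to change.** - Add current nursing or breastfeeding to the exclusion criteria under Research Design and Methods.
- Repeat it in the summary of criteria in section (1)(a).
- Ask about it once, in the screening history.

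The cost is one line, one matching phrase and one question. Nursing women could not enrol, which slightly reduces an already small number of women.
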